7.1.1 Permanent discontinuation

In rare instances, it may be necessary for a participant to permanently discontinue study intervention. If study intervention is permanently discontinued, the participant will remain in the study to be evaluated for the assessments planned for the EOT/EOS Visit, with the exception of the CT scan. See the SoA ([Section 1.3](#)) for data to be collected at the time of discontinuation of study intervention and follow-up and for any further evaluations that need to be completed.

Participants must be withdrawn from the study (ie, from any further IMP or study procedure) for the following reasons:

- At their own request or at the request of their LAR (an individual or judicial or other body authorized under applicable law to consent on behalf of a prospective participant to the participant's participation in the procedures involved in the research)
- If, in the Investigator's opinion, continuation in the study would be detrimental to the participant's well-being
- In case of surgery for NP
- At the specific request of the Sponsor
- In the event of a critical protocol deviation, at the request of the Investigator or the Sponsor
- In the event of an anaphylactic systemic allergic reaction that is related to IMP and that requires treatment
- In the event that the participant is diagnosed with a malignancy during the study, excluding carcinoma in situ of the cervix or squamous or basal cell
- Pregnancy
- Any opportunistic infection, such as TB or other infections whose nature or course may suggest an immunocompromised status (refer to Appendix 9 [[Section 10.9](#)])
- Met liver chemistry stopping criteria ([Section 7.1.2](#))

Handling of participants after permanent intervention discontinuation

Participants will be followed up according to the study procedures specified in this protocol up to the scheduled date of study completion or up to recovery or stabilization of any AE to be followed up as specified in this protocol, whichever comes last.

If possible, and after the permanent discontinuation of intervention, the participants will be assessed as soon as possible using the procedures normally planned for the EOT/EOS Visit (refer to SoA [[Section 1.3](#)]).

All cases of permanent intervention discontinuation must be recorded by the Investigator on the appropriate pages of the e-CRF when considered as confirmed.

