#### Change from baseline to Week 24 in LMK score

Computerized tomography (CT) scan should be performed anytime during the Screening Period before the first administration of IMP and at Visits 7 and 9 (Weeks 24 and 52). Whenever possible, a cone beam CT scan should be utilized.

Details for CT are available in a separate operational manual provided to the sites.

The LMK system is based on localization with points given for degree of opacification: 0 = normal, 1 = partial opacification, 2 = total opacification. These points are then applied to the maxillary, anterior ethmoid, posterior ethmoid, sphenoid, and frontal sinus on each side. The osteomeatal complex (OC) is graded as 0 = not occluded or 2 = occluded. Adding the scores of these 6 parameters will derive a maximum score of 12 per side (left and right). The total score of the 2 sides will be used for analysis. This scoring system has been validated in several studies(1)(2)(3).

For participants in whom the OC is missing (because of a previous surgery), the reader should consider the location of the previous OC and provide a score (as if the OC were there).

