#### **4.4.1.2 Main analytical approach**

##### Handling of missing data

Each of the 3 key secondary efficacy endpoints will be analyzed using the PP population and a hybrid method of worst observation carried forward (WOCF) and multiple imputation. For participants taking rescue medications or who undergo surgery, their data after the medication usage or surgery will be set to missing, and the worst postbaseline value on or before the time of the medication usage or surgery will be used to impute the missing Week 24 value. Participants who discontinue the treatment prematurely are encouraged to follow the planned clinical visits, and in those participants who did not take rescue medications or undergo surgery, all data collected after treatment discontinuation will be used in the analysis. For these participants, missing data may still happen despite all efforts to collect the data after treatment discontinuation. For participants who discontinue due to lack of efficacy, all data collected after discontinuation will be used in the analysis, and a WOCF approach will be used to impute the missing Week 24 value if needed. For participants who discontinue not due to lack of efficacy, a multiple imputation approach assuming missing at random will be used to impute the missing Week 24 value, and this multiple imputation will use all participants, excluding participants who have taken rescue medications or undergone surgery on or before Week 24 and excluding participants who discontinue due to lack of efficacy on or before Week 24. All of the imputed complete data will be analyzed by descriptive statistics with the 95% CI. The summarized mean changes obtained from each imputed dataset will be combined using Rubin's rule for a single estimate.

The following steps will be used to create the primary imputed datasets:

- Impute any missing baseline values with the mean baseline value of all participants with non-missing baseline data.
- For participants who are rescued (undergo surgery for NP or receive SCS for any reason) or discontinue treatment early due to lack of efficacy:
  - Set all data on or after earliest date of rescue or treatment discontinuation to missing.
  - Replace all missing values with the worst observation prior to the missing data through Week 24, including baseline values.
- For participants who are not rescued, discontinue treatment for reasons other than lack of efficacy, or complete the study:

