- Create 1 dataset with monotone missing pattern using the Markov Chain Monte Carlo (MCMC) method including values at all applicable visits through Week 24 in chronological order including baseline.
- For participants having missing data at Week 24 regardless of reason(s), a multiple imputation (MI) approach will be used to impute the missing endpoint value
- Set both datasets together.
- The remaining missing data will be imputed 40 times using the regression method for the monotone pattern with adjustment for values at all applicable visits through Week 24 in chronological order including baseline.
- Applying Rubin's rule to combine analysis results (means and standard errors) from 40 imputations using PROC MIANALYZE for the final estimated mean and 95% CL.

Missing data related to the key secondary endpoints will be tabulated including by relation to the COVID-19 pandemic. If necessary, additional supplementary analyses will be presented.

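### For unrescued participants who stop for reasons other than lack of efficacy (or miss the scan) and have no post-baseline CT, the Week 24 LMK imputation rests on baseline LMK only and leaves interim NPS unused

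*SAP*

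**What the plan says.** - **Imputation model.** SAP 4.4.1.2 gives one recipe for all three key secondary endpoints. After a step that makes the missing pattern monotone, the remaining gaps are filled 40 times by regression, "with adjustment for values at all applicable visits through Week 24 in chronological order including baseline". No variable other than the endpoint itself is named.
- **Who is multiply imputed.** "For participants who discontinue not due to lack of efficacy, a multiple imputation approach assuming missing at random will be used". The step list extends this to unrescued participants whose Week 24 value is missing for any reason.
- **Who is not.** For rescued participants (surgery or systemic corticosteroids) and lack-of-efficacy discontinuers, the instruction is worst observation carried forward (WOCF): "Replace all missing values with the worst observation prior to the missing data through Week 24, including baseline values".
- **CT schedule.** SAP 4.4.1.1 places the scan in the Screening Period "before the first administration of IMP and at Visits 7 and 9 (Weeks 24 and 52").
- **CT after discontinuation.** Protocol 7.1.1 says two things. A participant who stops permanently stays in the study to be "evaluated for the assessments planned for the EOT/EOS Visit, with the exception of the CT scan". Later in the section, "the participants will be assessed as soon as possible using the procedures normally planned for the EOT/EOS Visit", and the EOT/EOS column of the Schedule of Activities includes a CT.
- **Data after discontinuation.** "Participants who discontinue the treatment prematurely are encouraged to follow the planned clinical visits" (SAP 4.4.1.2), and what they contribute is used if they were not rescued.

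**The concern.** The recipe suits endpoints with several visits before Week 24. NPS is read at Weeks 4, 8 and 16 and the congestion diary is daily, so for those endpoints a participant's own course informs the imputed value. LMK has no scheduled value between screening and Week 24. A participant whose polyps had not responded by Week 16, and who then stopped for an adverse event or withdrew, is treated like any observed participant with the same baseline LMK.

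Missing at random given baseline LMK alone is a stronger assumption than missing at random given the polyp course as well. LMK is a key secondary endpoint meant to support similarity to dupilumab given with INCS. With no hypothesis test, the estimate and its interval carry the conclusion. The mITT supplementary analysis keeps the same missing-data rules, so it would not expose the problem. On the primary endpoint, by contrast, a missing Week 24 value counts as nonresponse.

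**Working it through.** **The plan's own figures.** With a true responder rate of 62% and n = 20, the probability of at least 10 responders is 0.908, which agrees with the stated 90%. Allowing for 20% drop-out, 20 / (1 - 0.20) = 25. Both reproduce. The documents give no LMK mean change, SD, missing rate or correlation with NPS, so every LMK figure below rests on assumptions.

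**What the model contains for LMK.** Missing baselines are first set to the mean, so the monotone step has nothing to do. The only applicable value before Week 24 is baseline LMK. This follows from the schedule; the SAP does not say it outright.

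**Size by arithmetic.** Let N be the number analysed, m the number imputed, D the completers' mean change and f the fraction of that benefit the imputed participants truly had, with baselines alike.

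- Expected estimate under the plan: [(N - m)D + mD] / N = D
- Truth: [(N - m)D + m f D] / N
- Overstatement of improvement: (m / N) x (1 - f) x |D|

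With N = 25 and an assumed D = -6:

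| m | f = 1 | f = 0.5 (shortfall 3) | f = 0.25 (shortfall 4.5) |
|---|---|---|---|
| 1 | 0 | 1/25 x 3 = 0.12 | 1/25 x 4.5 = 0.18 |
| 3 | 0 | 3/25 x 3 = 0.36 | 3/25 x 4.5 = 0.54 |
| 5 | 0 | 5/25 x 3 = 0.60 | 5/25 x 4.5 = 0.90 |

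Five is the whole 20% drop-out allowance. Simulation of the planned model (250 trials per scenario, 40 imputations) gave 0.64 and 0.94 for m = 5, and 0.41 for m = 3 with f = 0.5, close to the table. In the extreme case of no change at all (f = 0), with D = -3, -5 or -7, the overstatement is 0.12, 0.20 or 0.28 for one participant and 0.6, 1.0 or 1.4 for five. The LMK total runs from 0 to 24.

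**What NPS adds.**

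- Same setting, m = 5, with NPS change added: the bias fell from 0.64 to 0.30-0.40 (f = 0.5) and from 0.94 to 0.42-0.58 (f = 0.25), for an NPS-LMK correlation of 0.6 to 0.4. About half remained.
- A second simulation took the five missing from the participants with the least NPS improvement, with a mean LMK change of -5. At correlations 0.3, 0.5 and 0.7 the planned model overstated the mean by about 0.3, 0.6 and 0.8, and the model with NPS by about 0. At correlation 0 neither was biased. This is the favourable case for NPS, because NPS itself drove who was missing.

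**Which NPS value.** Using each participant's last available NPS compares completers' Week 24 value with stoppers' early values. Where stoppers follow the completers' course but stop before the full NPS response, this creates a bias the planned model does not have. One simulation gave up to 0.25 points. Another gave an understatement of 0.19 to 0.41, with RMSE rising from about 0.4 to 0.47-0.59. NPS taken at the same visit for everyone gave no bias in that case, less bias when stoppers do worse, and essentially equal or lower RMSE.

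**The case against.** A reader might infer that any discontinuer whose polyps did not shrink is credited with a completer's CT improvement. The documents do not support that:

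- Lack-of-efficacy discontinuers and participants given surgery or systemic corticosteroids get WOCF, which means zero LMK change if there is no earlier CT. Participants who use INCS before Week 24 leave the PP population.
- It is not settled that discontinuers lack a CT. The second statement in Protocol 7.1.1 points to a scan at discontinuation, and the CT column of SAP Table 10 accepts any scan after first dose up to Day 265 as Week 24. A discontinuer who attends Week 24 contributes an observed value.
- The prose of SAP 4.4.1.2 excludes WOCF participants from the imputation, but the steps combine the two datasets before the 40 imputations. If zero-change participants enter the regression, imputed values are pulled toward zero.

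It can also be said that nothing shows the remaining group (adverse events, COVID-19, withdrawal, a missed scan) does worse. The protocol expects permanent discontinuation to be rare and withdrawal uncommon, no LMK threshold exists, and the SAP allows further supplementary analyses if needed.

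All of this narrows the point and lowers its likely size. It does not remove it: for the group that is multiply imputed without a post-baseline CT, relevant data are collected and the planned model does not use them.

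**Conclusion.** The point holds in this limited form, as a low-cost improvement rather than a serious flaw. The bias is conditional, not established: zero if the imputed participants did as well as completers, about 0.1 to 0.2 LMK points for one such participant, and about 0.6 to 0.9 for the upper case of five of 25. These sizes assume a completer change of -6, half to one quarter of that benefit in those imputed, and no WOCF participants in the regression. Five also assumes that the entire drop-out allowance is unrescued, not efficacy-related and without a CT, which the documents do not suggest. The primary endpoint is untouched.

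**What to change.** 1. In SAP 4.4.1.2, for LMK only, add baseline NPS and NPS at matched scheduled visits (for example Weeks 8 and 16) to the imputation model, in chronological order, imputing later missing NPS first. Do not use a last-available NPS that mixes visits.
2. State that WOCF participants are left out of the regression, as the prose says, and amend the step that combines the datasets to match.
3. Reconcile the two statements in Protocol 7.1.1 on CT after permanent discontinuation, and say in the SAP how a scan taken then is used under Table 10.
4. Optionally, report a companion estimate giving zero change to unrescued discontinuers without a post-baseline CT, the value WOCF already gives to lack-of-efficacy discontinuers.

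The cost is a few extra terms in one model and perhaps one table line, with no new data. The downsides are a somewhat larger model at about 25 participants (baseline and Week 16 NPS alone would keep it smaller) and a small departure from the planned analysis, whose estimate can be reported alongside. A participant who stops before the first matched visit and has no further endoscopy gains little from the change.

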Key secondary endpoints	Change from baseline to Week 24: 
 
• Bilateral NPS
 
• NC symptom severity score
 
• LMK score
 
	PP	The intercurrent events will be handled as follows: 
 
• Taking rescue medications or undergo surgery prior to Week 24: data will be set to missing after the medication usage, and the participant's worst postbaseline value on or before the time of the medication usage or surgery will be used to impute the missing Week 24 value (for participants whose postbaseline values are all missing, the baseline will be used to impute) (hypothetical strategy)
 
• Discontinuing the treatment prematurely (Participants who did not take rescue medications or undergo surgery): all data collected after treatment discontinuation will be used in the analysis (treatment policy strategy).
 
	All imputed, complete data will be analyzed by descriptive statistics and 95% CI. The summarized mean changes obtained from each imputed dataset will be combined using Rubin's rule for a single estimate.

Estimands				
Endpoint Category	Endpoint	Population	Intercurrent event(s) handling strategy (The missing data handling)	Population-level summary (Analysis method)
Other secondary efficacy endpoints	
 
• Change from baseline to Week 24:
 
• Total symptom score
 
• Loss of smell symptom severity score
 
 Visual analogue scale for rhinosinusitis		In addition, the missing data imputation rules are as follows: 
 
• After treatment discontinuation due to lack of efficacy prior to Week 24: WOCF approach will be used to impute the missing Week 24 value if needed
 
• After treatment discontinuation due to reasons other than lack of efficacy prior to Week 24: multiple imputation approach assuming missing at random will be used to impute the missing Week 24 value, and this multiple imputation will use all participants, excluding participants who have taken rescue medications or undergone surgery on or before Week 24 and excluding participants who discontinue due to lack of efficacy on or before Week 24.
 
	

Estimands				
Endpoint Category	Endpoint	Population	Intercurrent event(s) handling strategy (The missing data handling)	Population-level summary (Analysis method)

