## 2 SAMPLE SIZE DETERMINATION

The EFC14280 study, which was conducted as a pivotal study for Nasal Polyposis, the proportion of responders (NPS improvement from baseline  $\geq 1$ ) at Week 24 was 62.0% in the dupilumab group. Based on this result, the target proportion of responders (NPS improvement from baseline  $\geq 1$ ) at Week 24 in this postmarketing study is at least 50.0% to reflect the similar effect size between EFC14280 and this study.

It is necessary for 20 participants to achieve this response rate (at least 50%) with a 90% probability of success. The sample size was adjusted up to 25 to account for a 20% drop-out rate.

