#### **4.4.2.2 Main analytic approach**

The supportive secondary efficacy endpoints (TSS, Loss of smell severity, VAS) will be analyzed using similar methodology as the key secondary endpoints using the PP population. Additionally, the number and percent of participants with VAS scores  $\leq 7$  cm will be presented using similar methodology for intercurrent events as the primary endpoint (Estimand 1).

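### SAP 4.4.1.2 gives no complete-data degrees of freedom for pooling the imputed results, so, run as written, the 95% limits for the secondary efficacy endpoints are near-normal and modestly too narrow for 20 to 25 participants

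*SAP*

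**What the plan says.** SAP 4.4.1.2 (Main analytical approach, key secondary endpoints) sets out the imputation in detail: one MCMC step to reach a monotone pattern, then 40 regression imputations. The last step is "Applying Rubin's rule to combine analysis results (means and standard errors"), taken "from 40 imputations using PROC MIANALYZE for the final estimated mean and 95% CL". The same section says of the imputed data: "All of the imputed complete data will be analyzed by descriptive statistics with the 95% CI". SAP Table 3 repeats this: "All imputed, complete data will be analyzed by descriptive statistics and 95% CI". Neither place says whether t or normal limits are meant. Protocol 9.3.3 describes the same pooling and is also silent on df.

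The method reaches further than the three key endpoints. Under SAP 4.4.2.2, TSS, loss of smell and VAS "will be analyzed using similar methodology as the key secondary endpoints using the PP population". SAP 4.4.1.3 and Table 3 apply the imputation to an mITT supplementary analysis of NPS, NC and LMK.

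The sample is small. SAP 2 states "It is necessary for 20 participants to achieve this response rate (at least 50%) with a 90% probability of success" and then "The sample size was adjusted up to 25 to account for a 20% drop-out rate".

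The primary endpoint, by contrast, has a named interval: SAP 4.3.2 specifies a continuity-corrected Wilson interval.

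**The concern.** A mean and its standard error carry no information about sample size. If these are all that the pooling step receives, the df come from the number of imputations and the spread between them, and the size of the trial does not enter. With 40 imputations and modest missingness, the df run to hundreds or thousands and the limits are in effect normal. With 20 to 25 participants, the SD is itself estimated from few values and a t multiplier is needed.

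The trial tests no hypothesis, so its results are estimates and intervals. Protocol 3.1 and 4.2.2 say that the key secondary endpoints are to show efficacy similar to dupilumab with INCS. Limits labelled 95% should therefore have about that coverage. The shortfall in the multiplier is present even when little is missing. The design makes a small multiple-imputation component plausible: participants who are rescued or who stop for lack of efficacy get one carried-forward worst value, and a missing baseline gets the mean. Neither adds between-imputation variance.

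**Working it through.** **Inputs from the documents.** m = 40 imputations and 95% limits (SAP 4.4.1.2). The reference study's responder rate "at Week 24 was 62.0% in the dupilumab group"; target at least 50%; 20 evaluable; 25 enrolled; 20% drop-out (SAP 2).

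**Assumed input.** The relative increase in variance from missingness, r, is not in the documents. I use r = 0.02 to 0.30, which is a missing-information share λ = r/(1+r) of about 0.02 to 0.23.

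**The plan's own figure.** With a true rate of 0.62, P(at least 10 of 20 respond) = 0.908 by the exact binomial, against the stated 90%. Also 20/(1 - 0.20) = 25. Both reproduce, so 20 and 25 are the right sizes to examine. The SAP states no precision figure for the secondary endpoints.

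**Step 1: df with no complete-data df supplied.** The formula is df = (m-1)(1+1/r)², which does not contain n.
- r = 0.05: 39 × 21² = 17,199; multiplier 1.960.
- r = 0.30: 39 × (1 + 1/0.30)² = 732; multiplier 1.963.

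**Step 2: nothing imputed.** The benchmark is t with n-1 df.
- n = 20: t(19) = 2.093. 1 - 1.960/2.093 = 6.4% too narrow. Coverage of a 1.96 interval is 93.5%.
- n = 25: t(24) = 2.064. 1 - 1.960/2.064 = 5.0% too narrow. Coverage is 93.8%.

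**Step 3: some values imputed.** The benchmark is the Barnard-Rubin df. With d = n-1, the observed-data df is d(1-λ)(d+1)/(d+3). This is combined with the Step 1 df by adding reciprocals and inverting.

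| n | r | Barnard-Rubin df | Multiplier | Multiplier as written | Narrower by |
|---|---|---|---|---|---|
| 20 | 0.02 | 16.9 | 2.111 | 1.960 | 7.1% |
| 20 | 0.30 | 13.1 | 2.159 | 1.963 | 9.1% |
| 25 | 0.02 | 21.8 | 2.075 | 1.960 | 5.5% |
| 25 | 0.30 | 16.7 | 2.113 | 1.963 | 7.1% |

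The SD cancels in these ratios, so they hold for any of the six endpoints.

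**Step 4: coverage by simulation.** The data were normal, with regression imputation, m = 40 and correlation 0.3 between baseline and Week 24 (all assumed), and 6,000 runs per case.

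| n | Missing | Coverage as written | Coverage with Barnard-Rubin df |
|---|---|---|---|
| 20 | 0% | 93.4% | 95.0% |
| 25 | 0% | 93.8% | 95.1% |
| 20 | 10% | 93.7% | 95.5% |
| 25 | 12% | 94.4% | 95.6% |
| 20 | 20% | 94.4% | 96.0% |
| 25 | 20% | 94.2% | 95.6% |

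A second simulation, with five visits, NPS-like normal data and monotone drop-out (3,000 runs), gave 94.1 to 94.4% at 5% drop-out, 94.2 to 94.8% at 10%, and about 95% at 20%. Coverage recovers there because the imputation variance is itself conservative at this sample size.

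**The case against.** **The SAP is silent; it does not exclude a small-sample df.** A programmer could supply the complete-data df and the problem would disappear. This stands, and it is why the point is conditional on the step being run as written. A reader might infer that the plan has chosen to disregard the small sample; the text does not support that. Still, the SAP specifies the rest of the algorithm closely, and following its stated inputs literally gives the narrow limits.

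**Not every secondary endpoint is affected.** TEAE, TESAE and discontinuation incidence are secondary endpoints too (SAP Table 2) and are not pooled this way. The point covers the six efficacy endpoints only.

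**The pooled limits are not the only information on precision.** A reader might infer that they are. SAP 4.5.2.3 also summarises the endpoints by visit without imputation, and SAP 4.1 calls for descriptive statistics by visit in PP and mITT. If these include n, mean and SD, as the SAP's other continuous summaries do, a t interval on observed data can be formed from them.

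**The width figures look larger than their effect.** This is largely right. Drop-outs are imputed and stay in the PP population, so 25 enrolled with 20% drop-out means n near 25. The 9% end needs n = 20 together with substantial imputation, which would take under-enrolment or exclusions for INCS use. At 20% drop-out the coverage loss is one point or less. The simulations also omit the carried-forward values, the single MCMC completion and the bounded NPS scale, so actual coverage is not established.

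**Nothing is decided on these intervals.** Correct. There is no test, margin or interval-based success rule, and the comparison with EFC14280 in protocol section 9 rests on point estimates of the responder proportion.

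**Conclusion.** The point holds as a minor one. If no complete-data df is supplied, the pooled 95% limits for NPS, NC, LMK, TSS, loss of smell and VAS use a multiplier of about 1.96 in a trial of 20 to 25 participants. They are then 5.0 to 6.4% narrower than the t interval with nothing imputed, and about 5.5 to 9% narrower than Barnard-Rubin limits with imputation. Coverage is about 93.5 to 94.5% at low missingness and about 94 to 95% at 20% drop-out.

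This rests on three assumptions: pooling from means and standard errors alone, a relative variance increase of 0.02 to 0.30, and normal data in the simulations. A reader might infer that the conclusions on similarity to EFC14280 are at risk. They are not: the point estimates do not change, and neither the primary endpoint's Wilson interval nor any decision rule depends on this step.

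**What to change.** Add to SAP 4.4.1.2 that the pooled 95% limits use the Barnard-Rubin small-sample df, with complete-data df equal to n-1 for each endpoint in the population analysed (EDF = n-1 in PROC MIANALYZE). Add that the ordinary t interval with n-1 df is reported for any endpoint with no imputed value. State that the same rule applies to the supportive secondary endpoints (SAP 4.4.2.2) and to the mITT supplementary analysis (SAP 4.4.1.3).

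The cost is one option in the program and a sentence or two in the SAP. No new data are needed and the point estimates stay the same. The intervals become about 5 to 10% wider: 2.064/1.960 = 1.053 at n = 25 with nothing imputed, and 2.159/1.963 = 1.10 at n = 20 with r = 0.30. When much is imputed they are slightly conservative, with simulated coverage up to 96.0%.
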